2.1.4. Analysis Sets

2.1.4.1. Treated Analysis Set

The Treated analysis set is defined as all subjects who receive at least 1 dose of study drug. It will be used as both the primary efficacy analysis set and safety analysis set.

2.1.4.2. Intent-to-Treat Analysis Set

The Intent-to-Treat (ITT) analysis set is defined as all subjects randomized into the study and who will be classified according to their assigned treatment group. It will be used for analyses of disposition, demographic, and baseline disease characteristics.

2.1.4.3. Biomarker Analysis Set

The Biomarker analysis set is defined as all subjects who receive at least 1 dose of study drug and have at least one post baseline biomarker assessment done.

2.1.4.4. Treated for Week 12/24 Analysis Set

The Treated for Week 12/24 analysis set is defined as all subjects who receive at least 1 dose of study drug with an observed measurement collected at week 12/24.

2.1.4.5. Definition of Subgroup

Subgroup analysis will be performed for the selected variables to assess the internal consistency of the treatment benefit and/or safety. The subgroup variables and the cutoff values are subject to change if warranted to better represent the data. Additional subgroup analyses (not limited to groups specified in table below) may be performed as ad-hoc exploratory analyses.

Subgroup	Definition of Group	Analysis Type
Risk	Intermediate 2, High risk	S ^(a)
Sex	Male, Female	S
Race	White, Asian, Other	S
Age	≤65, >65	S

^a S: Safety (adverse events)

2.1.5. Other General Definitions

2.1.5.1. Individual Study Start/Treatment Start (Day 1), Study Day and Month

Individual Study Start /Treatment start is the date of the Cycle 1, Day 1. If study drug was not administered to a subject, study start is defined as the date of randomization.

The study day is equal to the date of the procedure minus the date of study start plus 1.

A month is defined as 365.25/12 days.

2.1.5.2. End of Treatment, End of Study, Time on Treatment , and Time on Study for Individual Subject

For each individual subject, disposition definitions are defined as below:

End of treatment is defined as the date of the last dose of the study drug. The end of Study is the date of death or the date last known to be alive, defined as the maximum date of the following study evaluations: randomization, vital signs, ECOG performance status, MRIs, physical examination, bone marrow evaluations, labs (hematology, chemistry), study drug administration, subsequent therapy, investigator-assessed PD, relapse from CR, investigator determined response, and survival follow-up.

The treatment cycle is defined as 21 days.

Time on treatment (in weeks) is equal to (the end date of treatment – the date of Cycle 1, Day 1 + 1)/7.

Time on study (in months) is equal to (the end date of follow-up – the date of Cycle 1, Day 1 + 1)/30.4375.

2.1.5.3. Number of Treatment Cycles Received

The number of cycles received is the number of treatment cycles in which there is at least 1 nonzero dose of the study drug.

2.1.5.4. Properties of Treatment Cycles

For each treatment cycle, the following variables are to be derived.

- Cycle delay (≥ 4 days) — to flag if this cycle is delayed 4 or more days (date of Day 1 in the current cycle – date of Day 1 in the previous cycle is ≥ 25 days) and checked on the case report form (CRF) by investigator as cycle delayed.
- Reasons for cycle delay (≥ 4 days) — to record reasons for cycle delay (≥ 4 days) on the CRF.
- Dose reduction — to flag if the prescribed dose of the study drug is reduced at least once relative to the previous nonzero dose for study drug.
- Reasons for dose reduction — to record reasons for dose reduction on the CRF.
- Dose withholding — to flag if the dose of the study drug is withheld at least once. The number of doses withheld will also be recorded.
- Reasons for dose withholding — to record reasons for dose withholding on the CRF. Reasons for dose withholding will be recorded for each separate dose withholding incident.
- Dose modification — to flag if the dose of the study drug is modified (delayed, reduced, withheld) at least once for study drug.
- Reasons for dose modification - to record reasons for dose modification.
- Number of administered doses — to record the number of nonzero doses actually administered to a subject for study drug.
- Total dose (mg/kg) — to record the sum of nonzero doses actually administered to a subject for study drug.
- Total planned dose (mg/kg) — to record the sum of planned nonzero doses for study drug.
- Dose interval – days between two consecutive dosing dates.

2.1.5.5. Dose Intensity and Relative Dose Intensity

Dose intensity (mg/kg/cycle) will be calculated for study drug by cycle and overall.

The overall dose intensity is equal to the sum of the total dose (mg/kg) received in all cycles divided by the number of cycle received.

The dose intensity per cycle is equal to the sum of the total dose (mg/kg) received in that cycle.

The overall planned dose intensity is equal to the sum of the planned total dose (mg/kg) in all cycles divided by the number of cycles received.

The planned dose intensity per cycle is equal to the sum of the planned total dose (mg/kg) in the cycle.

The relative dose intensity is the ratio of the dose intensity and the planned dose intensity.

2.1.5.6. Age and Age Categories

Age will be calculated at the date of informed consent and integer values will be used. If the date of informed consent is not available, the date of randomization will be used. The following categories of age will be used: ≤ 65 years, > 65 years.

2.1.5.7. Baseline Values and Subject Disease Characteristics

Refer to Section 2.1.1 for the definition of baseline values. Below are some of key disease characteristics.

Bone Marrow Assessments at Baseline

A bone marrow biopsy/aspirate will be performed for all subjects at baseline. Outcomes of bone marrow assessments (Degree of Cellularity, Degree of Fibrosis, and Blasts) will be reported and captured on eCRF.

Myelofibrosis Symptoms (modified MFSAF v2.0)

Myelofibrosis symptoms will be collected at baseline and recorded on the CRF for each item of the questionnaire with possible scores of 0-10.

MF Type

Myelofibrosis type will be collected at baseline and recorded on the CRF as Primary MF, post-ET-MF(PET), and post-PV-MF(PPV).

DIPPS Risk Scores

Dynamic International Prognostic Scoring System (DIPSS) risk score will be collected at baseline and recorded on the CRF (int-2, high).

Time Since Initial Diagnosis

Time since initial diagnosis is defined for all subjects and is calculated from the date of diagnosis to the date of randomization (month).

2.1.5.8. Concomitant Medication

Concomitant medications during study treatment include only those concomitant medication records that are indicated on the CRF as not being prior therapy, and have the onset date, possibly imputed, no earlier than treatment start and no later than treatment end. Concomitant medications include all concomitant medications administered during the study, including those indicated on the CRF at study entry.

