8. PRESTUDY AND CONCOMITANT THERAPY

All recommendations regarding the use of concomitant therapy are applicable to the Extension Phase.

All subjects receiving imetelstat must be premedicated with diphenhydramine (25 to 50 mg) and hydrocortisone (100 to 200 mg), or equivalent. It is recommended that subjects are monitored for at least 1 hour after the infusion has been completed.

Subjects may receive supportive care as clinically indicated. This includes blood product support (blood transfusions and the use of granulocyte colony stimulating growth factors), anti-diarrheals, anti-emetics, analgesics, antibiotic treatment, and treatment of other medical conditions.

The following medications are prohibited during the study: chemotherapy (anticancer) or MF-directed therapy, immunotherapy, experimental therapy, and radiotherapy. Systemic use of corticosteroids in excess of prednisone 20 mg/day or its equivalent for more than 10 days is prohibited unless reviewed and approved by the sponsor's medical monitor. Long-term, chronic use of corticosteroids at any dose also should be reviewed and approved by the sponsor's medical monitor. Corticosteroids used as premedication are permitted. The sponsor must be notified in advance (or as soon as possible, thereafter) of any instances in which prohibited therapies are administered.

Prestudy therapies administered up to 30 days before first dose of study drug must be recorded at screening. Transfusions up to 12 weeks prior to baseline also must be recorded at screening.

Concomitant therapies (prescription or over-the-counter medications, including vaccines, vitamins, herbal supplements), including growth factors, transfusions, anti-infectives (antibacterials, antivirals, and antimycotics), steroids, anti-arrhythmics and other cardiac supportive therapy, anti-histamines, anti-emetics, anti-diarrheals, and anti-coagulants must be recorded throughout the study beginning with signing of the ICF to 30 days after the last dose of study drug or until the start of subsequent anticancer treatment, if earlier. Modification of an effective preexisting therapy should not be made for the explicit purpose of entering a subject into the study. Concomitant therapies should be recorded beyond 30 days only in conjunction with new or worsening adverse events or serious adverse events that meet the criteria outlined in Section 12.3.2, Serious Adverse Events.

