2.3.7. Concomitant Medications

Concomitant therapies other than antineoplastic agents or other systemic therapies for MF, post ET-MF, and post PV-MF after randomization will be classified by preferred WHO Anatomical Therapeutic Chemical (ATC) and summarized by therapeutic class and pharmacological class. Separate analyses will be performed for concomitant medications started during treatment and for all concomitant medications use (including baseline use).

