2.3.9.1. Adverse Events

Treatment-emergent adverse events are defined as any adverse event that occurs after administration of the first dose of study drug and through 30 days after the last dose of study drug, any event that is considered drug-related (possibly, probably, or possibly related) regardless of the start date of the event, or any event that is present at baseline but worsens in intensity or is subsequently considered drug-related by the investigator. The severity of adverse events will be assessed using NCI CTCAE Version 4.0.

The Medical Dictionary for Regulatory Activities (MedDRA version 20.0) dictionary will be used to code the investigator's adverse event terms to preferred term and system organ class. Adverse event tables will summarize incidence by the treatment arm actually received.

For each AE, its relationship to study drug is determined by the investigator and recorded on the CRF. An adverse event is considered as related to study drug if it is possibly, probably, or very likely related to study drug imetelstat.

An overview of treatment-emergent adverse events as well as the incidence of treatment-emergent adverse event will be summarized. The following tabulations will also be presented:

- Incidence of treatment-emergent adverse events by system organ class and preferred term.
- Incidence of treatment-emergent adverse events, especially the most commonly reported events, ie, those events reported by at least 5% of subjects, by MedDRA system organ class and preferred term.
- Incidence of treatment-emergent adverse events considered by the investigator to be related to study drug, by system organ class and preferred term.
- Incidence of treatment-emergent adverse events by CTCAE toxicity grade.
- Incidence of treatment-emergent adverse events leading to withdrawal from treatment by system organ class and preferred term (adverse events leading to discontinuation of all study drugs).
- Incidence of treatment-emergent adverse events leading to death by system organ class and preferred term.

For treatment-emergent adverse events with CTCAE toxicity Grade 3, 4, or 5, the following summaries are to be produced:

- Incidence of Grade 3, 4, or 5 treatment-emergent adverse events, by system organ class and preferred term.
- Incidence of Grade 3, 4, or 5 treatment-emergent adverse events considered by the investigator to be related to study drug, by system organ class and preferred term.

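### The SAP closes the on-treatment medication table at the last infusion, so supportive drugs started in the following 30 days appear only in the all-use table

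*SAP*

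**What the plan says.** SAP 2.1.5.8 defines medications during study treatment as records not marked as prior therapy whose onset date is "no earlier than treatment start and no later than treatment end". The only definition of the closing date is in SAP 2.1.5.2: "End of treatment is defined as the date of the last dose of the study drug". Under SAP 2.1.5.1, "Individual Study Start /Treatment start is the date of the Cycle 1, Day 1". SAP 2.1.1 fits this reading, because it starts posttreatment follow-up on the day after the drug is discontinued.

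SAP 2.3.7 builds two summaries: "Separate analyses will be performed for concomitant medications started during treatment", and a second for all use, baseline included. SAP 2.1.5.8 gives that second group no closing date short of the study itself.

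Other safety windows are longer. Treatment-emergent adverse events count "through 30 days after the last dose of study drug" (SAP 2.3.9.1). Laboratory data are reported to the same day (SAP 2.3.9.3), and deaths within 30 days of the last dose are tabulated (SAP 2.3.9.2). Protocol Section 8 records concomitant therapies from consent "to 30 days after the last dose of study drug or until the start of subsequent anticancer treatment, if earlier".

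**The concern.** The drug is infused once per cycle, and "The treatment cycle is defined as 21 days" (SAP 2.1.5.2). The last infusion date is therefore the first day of the last cycle, not its end. Supportive treatment begun the next day, for toxicity of that dose, is already outside the on-treatment table, while the adverse event it treats is inside the treatment-emergent table.

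The rule also makes inclusion depend on what happens later. Protocol Section 6 allows the drug to be held, and provides for permanent discontinuation, unless the sponsor approves otherwise, when toxicity prevents a restart within 21 days. A drug begun during a hold is counted if the subject is dosed again, because the later dose moves the closing date. It is excluded if the subject never restarts. The on-treatment table therefore under-counts support given for toxicity that ended treatment. Protocol Section 1.1.5.3.1 describes cytopenias as dose-limiting, and Section 6 permits G-CSF for neutropenia, so this is a foreseeable use of the table.

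**Working it through.** The plan gives no figure of its own to reproduce. The check traces the definitions and then counts days.

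**Inputs**
- Window opens at Cycle 1, Day 1 (SAP 2.1.5.1).
- Window closes at the last dose (SAP 2.1.5.2 with 2.1.5.8).
- Cycle length is 21 days (SAP 2.1.5.2). Assumption: no delays.
- Comparison window closes 30 days after the last dose (SAP 2.3.9.1).
- Illustrative numbers of cycles: 1 and 4, the minimum and median at the first interim review (Protocol 3.2.1), and 12, the median behind the blood-volume planning (Protocol 9.1.1, Table 8 footnote).

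**Formulas**, for *n* cycles:
- On-treatment medication window = 21(*n* − 1) + 1 days.
- Window to 30 days after the last dose = 21(*n* − 1) + 31 days.
- Share outside the medication window = 30 / [21(*n* − 1) + 31].

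| Cycles | Medication window (days) | Window to last dose + 30 (days) | Share of days outside |
|---|---|---|---|
| 1 | 0 + 1 = 1 | 31 | 30/31 = 97% |
| 4 | 63 + 1 = 64 | 94 | 30/94 = 32% |
| 12 | 231 + 1 = 232 | 262 | 30/262 = 11% |

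**Dependence on re-dosing** (hypothetical dates). Two subjects are dosed on Days 1 and 22. The third dose, due on Day 22 + 21 = 43, is held for both, and both start G-CSF on Day 45.
- The first resumes on Day 57, 14 days after the due date. End of treatment is Day 57 or later, so Day 45 is inside the window and the G-CSF is counted.
- The second never resumes. End of treatment is Day 22, so the G-CSF is excluded. Day 45 is still before Day 22 + 30 = 52, so the adverse event window covers it, and so does medication collection unless subsequent anticancer treatment has begun.

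**The case against.** The strongest reply is that the SAP is internally consistent. A table of drugs started during treatment that stops when treatment stops follows the phase structure of SAP 2.1.1, and the SAP writes a 30-day tail where it wants one. Protocol Section 8 sets a collection window and does not oblige any table to span it. This stands: the two documents do not contradict each other, and a narrow window could be deliberate. But the SAP gives no reason for it, and dependence on later re-dosing is an odd property for an intended definition.

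A reader might infer that the post-dose records are lost. They are not. They are collected and belong in the all-use table, although nothing there marks them as started after the last dose.

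A reader might also take 97% or 32% as the share of medications missed. The documents give no counts of medications started after the last dose, so only days can be compared. The four-cycle median was taken while enrollment was still open, whereas this SAP covers a cutoff 18 months after the last enrollment. The twelve-cycle planning value gives about 11%. Neither is the final median.

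Finally, it would be too strong to say that the medication and adverse event tables cannot be read together. No planned analysis links them. Their windows simply differ by up to 30 days.

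**Conclusion.** The point holds as a minor misalignment in safety reporting. As defined, the on-treatment medication table excludes supportive drugs started in the 30 days after the last dose. The excluded part of the window is 30 of 31 days for one cycle, 30 of 94 for four and 30 of 262 for twelve, assuming 21-day cycles without delay.

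The gap has limits:
- It is shorter where subsequent anticancer treatment starts within the 30 days, because medication collection generally stops there.
- It does not arise for subjects still on treatment at cutoff, who have no completed tail.
- It does not arise from the final dose of Arm B subjects whose dose was escalated, because SAP 2.1.3 ends their tabulated data at escalation.
- G-CSF and antibiotics are the firm examples. The SAP does not say whether transfusions enter the table coded by therapeutic class.

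That the shortfall is largest among subjects who stopped early for toxicity is plausible from the rule, but the documents contain no data to show it. There is no effect on the co-primary endpoints.

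**What to change.** In SAP 2.1.5.8, replace the upper limit at treatment end with the limit in Protocol Section 8: "to 30 days after the last dose of study drug or until the start of subsequent anticancer treatment, if earlier". Relabel the SAP 2.3.7 table as treatment-emergent, or as medications started during treatment or within 30 days after the last dose.

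This matches the protocol's collection window. It matches the adverse event window except where subsequent anticancer treatment starts early, because the treatment-emergent definition has no such stop. The small downside is that the table will include starts that SAP 2.1.1 places in posttreatment follow-up, which is why the label has to change as well.

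If the narrow window is intended, the SAP should say so and add a table of medications started from the day after the last dose to Day 30. Either route costs a derivation line and a table title, or one extra table, and needs no new data.

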2.1.5.9. Protocol Deviations

Subjects with major protocol deviations including eligibility will be listed by treatment arm. Major protocol deviations include: developed withdrawal criteria but not withdrawn, entered but did not satisfy criteria, received a disallowed concomitant treatment, received wrong treatment or incorrect dose, and other.

Protocol deviations will be based on clinical review, but not limited to, the following aspects: (1) eligibility criteria, (2) patient safety, (3) efficacy assessment deviation, (4) treatment compliance. Protocol deviations will be closely monitored during the execution of the study and the final set of protocol deviation criteria will be finalized before database lock.

2.2. Interim Analyses and Data Review Committee

2.2.1. Interim Analyses

There were two interim analyses planned in this study. The first interim review analysis was performed when the first 40 evaluable subjects defined as the subjects who had both baseline and post baseline spleen measurement per investigator MRI, (20 per treatment arm) were followed for at least 12 weeks. The second interim review was performed with a clinical cutoff that was 6 months after the clinical cutoff used for the first interim review.

The goals of the interim reviews were to assess safety and early efficacy and perform comprehensive exposure-response analyses. Based on these analysis, if both doses were efficacious and had an acceptable safety profile, both arms would continue with

enrollment until approximately 100 subjects per arm were enrolled. If only one dose was efficacious and had an acceptable safety profile, then that arm would continue enrollment and enrollment would be stopped in the other arm. In the case that both arms were not efficacious and safe, an alternative dose may be selected based on the PK/PD exposure-response, efficacy, and safety analysis and a protocol amendment would be implemented to reflect this. Study enrollment would continue at the time of interim reviews.

Safety would be evaluated using the following parameters (including but not limited to): adverse events, serious adverse events, dose modifications and subject compliance. PK/PD exposure-response analyses for efficacy parameters (eg, SVR from baseline at Week 12), and for safety parameters (e.g., platelets and hemoglobin) would be conducted. Biomarkers such as change in TA, TL and hTERT from baseline may be evaluated for subjects with available data.

Early efficacy would be evaluated by SVR by MRI and as assessed by the investigator.

[REDACTED]

Other efficacy data including symptoms, peripheral blood counts and bone marrow data up to interim will be reviewed as well. This guideline is intended to inform the decision, which is expected to be multifactorial taking into consideration safety, tolerability, and PK/PD modeling.

2.2.2. Data Review Committees

A sponsor Data Review Committee (DRC) was formed to monitor data on a regular basis to ensure the safety of the subjects in this study, assess the evidence of benefit or adverse effects of imetelstat, and to monitor the overall conduct of the study. The DRC would consist of at least one medical expert in the relevant therapeutic area and at least one statistician. At an interim analysis, all available data (e.g. pharmacokinetics [PK], safety, efficacy, pharmacodynamics [PD] biomarkers: TA, TL or hTERT) would be assessed, and integrated exposure-response analyses with PK/PD, safety and efficacy modeling would be conducted. Response data assessed by the investigator up to the cutoff date would be used for the interim review. Based on these analyses, the DRC

would determine if enrollment in one or both treatment arms should continue, or if an alternative dose should be selected for further development. The DRC is responsible for monitoring and reviewing the safety data approximately every 3 months or at an agreed upon review interval until all patients discontinued from study treatment and the post treatment follow up phase, and at the time of interim review stated above. The review consists of at minimum, summaries of overall rates of deaths, serious adverse events (SAEs), and all adverse events and relevant laboratory test data. Details (responsibilities, authorities, procedures) are provided in the DRC Charter.

An independent Hepatic Expert Committee (HEC) was formed to assess/identify hepatic risk in study. The HEC would consist of at least two physicians. The DRC and HEC are not blinded to the treatment throughout the study. A central Independent Review committee (IRC) was formed to assess spleen volume based on MRI scans performed. The IRC would consist of reviewers who are experts in reading MRI scans from Paraxel/Perceptive. The IRC reviewers were blinded to the treatment throughout the study.

